11.3 Safety reviews

11.3.1 Safety considerations for Part A dose escalation

The HVTN 143/HPTN 109 PSRT will monitor participant safety data throughout the study and as described in this section and in Table 11-1 below. To determine if enrollment may commence in subsequent groups for dose escalation, the HVTN 143/HPTN 109 PSRT will review study safety data and will consider all available safety data on the Abs used in this study, including from ongoing and concurrent clinical trials (eg, VRC615).

11.4 Safety considerations for Part A dose escalation

The trial will begin with enrollment in Part A Group 1 only, then Group 2 only, and then Group 3. Additional participants may be enrolled in each group to ensure the availability of safety data from at least 5 participants in each group.

Enrollment will start with Group 1 and will be restricted to a maximum of 1 participant per day across all participating CRSs until a total of 5 participants have been enrolled. Enrollment will then be held. The HVTN 143/HPTN 109 PSRT will review safety data, as described in Table 11-1. Upon PSRT determination that it is safe to proceed, enrollment in Group 2 will begin.

Enrollment in Group 2 will be restricted to a maximum of 1 participant per day across all participating CRSs until a total of 5 participants have been enrolled. Enrollment will then be held. The HVTN 143/HPTN 109 PSRT will review safety data, as described in Table 11-1. Upon PSRT determination that it is safe to proceed, enrollment in Group 3 will begin.

Enrollment in Group 3 will be restricted to a maximum of 1 participant per day across all participating CRSs until a total of 5 participants have been enrolled.

11.4.1 Safety evaluation for moving from Part A to Part B

The HVTN 143/HPTN 109 PSRT will review safety data, including from Groups 1 through 3, as described in Table 11-1. The HVTN 143/HPTN 109 PSRT will make a decision regarding the appropriateness of allowing enrollment into Part B. If any \geq Grade 3 AE(s) deemed related to study product are reported in Part A, the HVTN SMB will perform an additional review of this safety data to make the final determination based on safety for proceeding to Part B.

In Part B, Groups 4, 5, 6, 7, and 8 will enroll simultaneously without restrictions.

Planned safety hold #	Group(s)	Timepoint/data reviewed	Action
1	1	Begins after the fifth participant is enrolled (infused) in Group 1 and the solicited AE assessment data through the day 7 visit is reported.Review of all cumulative safety data available for the 5 participants in Group 1, up to and including the solicited AE assessment data reported at the day 7 visit after the study-product administration.	The PSRT will decide the appropriateness of beginning enrollment in Group 2 based on these safety data.
2	2	Begins after the fifth participant is enrolled (infused) in Group 2 and the solicited AE assessment data through the day 7 visit is reported. Review of all cumulative safety data available, including the first 5 participants in Group 2, up to and including the solicited AE assessment data reported at the day 7 visit after the study-product administration.	The PSRT will decide the appropriateness of beginning enrollment in Group 3 based on these safety data.
3	1-3	Begins after the fifth participant is enrolled (infused) and the solicited AE assessment data through the day 7 visit is reported (5 participants each in Groups 1, 2, and 3). Review of all cumulative safety data available for all participants in Part A (groups 1-3), up to and including the solicited AE assessment data reported at the day 7 visit after the product administration for participants in Group 3.	The PSRT (+/- SMB) will decide the appropriateness of beginning unrestricted enrollment in Part B based on all available safety data from all participants included in Part A.

Table 11-1 Summary of planned safety holds and safety data reviews for dose escalations

Note: Additional participants may be enrolled in each group to ensure the availability of safety data from at least 5 participants in each group.

11.5 Safety pause and prompt PSRT AE review

When a trial is placed on safety pause, all enrollment and study-product administration with the product related to the event that triggered the pause will be held until further notice. The AEs that will lead to a safety pause or prompt HVTN 143/HPTN 109 PSRT AE review are summarized in Table 11-2. Studyproduct administrations may be suspended for safety concerns other than those described in the table, or before pause rules are met, if, in the judgment of the HVTN 143/HPTN 109 PSRT, participant safety may be threatened. Criteria for an individual participant's departure from the schedule of study-product administrations are listed in Section 7.3.

Event and relationship to study products	Severity	CRS action ^a	HVTN LOC action ^b
SAE, related	Grade 5 or Grade 4	Phone immediately, email and submit forms immediately	Immediate pause
SAE, not related	Grade 5	Phone immediately, email and submit forms immediately	Immediate PSRT notification
SAE, related	Grade 3, 2, or 1	Email and submit forms immediately	Immediate PSRT notification and prompt PSRT AE review to consider pause
AE ^c , related	Grade 4 or 3	Email and submit forms immediately	Immediate PSRT notification and prompt PSRT AE review to consider pause

^a Phone numbers and email addresses are found on the protocol home page on the HVTN Members' site (https://members.hvtn.org/protocols/hvtn143-hptn109).

^b HVTN CSS or RML or other HVTN Core designee

^c Does not include subjective solicited AEs (infusion-site pain and/or tenderness, fatigue/malaise, myalgia, arthralgia, chills, headache, nausea [unless IV rehydration required], nonexertional dyspnea, generalized pruritus, facial flushing, and unexplained diaphoresis).

For all safety pauses, HVTN LOC notifies the HVTN 143/HPTN 109 PSRT, HVTN Regulatory Affairs, DAIDS Pharmaceutical Affairs Branch (PAB), DAIDS Regulatory Affairs Branch (RAB), DAIDS Safety and Pharmacovigilance Team (SPT), and participating CRSs. When an immediate safety pause is triggered, HVTN LOC notifies the SMB.

Once a trial is paused, the HVTN 143/HPTN 109 PSRT reviews safety data and decides whether the pause can be lifted or if permanent discontinuation of study product administration is appropriate, consulting the SMB if necessary. The HVTN LOC notifies the participating CRSs, HVTN Regulatory Affairs, DAIDS PAB, DAIDS RAB, and DAIDS SPT of the decision regarding resumption or discontinuation of study-product administrations. Based on the HVTN 143/HPTN 109 PSRT assessment.

If an immediate HVTN 143/HPTN 109 PSRT notification or prompt HVTN 143/HPTN 109 PSRT AE review is triggered, HVTN Core notifies the HVTN 143/HPTN 109 PSRT as soon as possible during working hours (local time) or, if the information was received during off-hours, by the morning of the next workday. If a prompt HVTN 143/HPTN 109 PSRT AE review cannot be completed within 72 hours of notification (excluding weekends and US federal holidays), an automatic safety pause occurs.

The HVTN and HPTN require that each CRS submit to its IRB/EC and any applicable RE protocol-related safety information (such as IND safety reports, notification of study-product holds due to the pause rules, unanticipated problems involving risks to participants or others, and notification of other unplanned safety pauses). CRSs must also follow all applicable RE reporting requirements.

In addition, all other AEs are reviewed routinely by the HVTN 143/HPTN 109 PSRT (see Section 11.6.2).

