7.3.3 Discontinuing study-product administration for a participant

Under certain circumstances, an individual participant's study-product administrations will be permanently discontinued. Specific events that will result in stopping a participant's study-product administration schedule include:

- Coenrollment in a study with an investigational research agent (rare exceptions allowing for the continuation of study-product administrations may be granted with the unanimous consent of the HVTN 143/HPTN 109 PSRT)
- Clinically significant condition (ie, a condition that affects the immune system or for which continued study-product administrations and/or blood draws may pose additional risk), including but not limited to the following:
 - HIV acquisition
 - Any grade 4 local or systemic solicited or unsolicited AE that is subsequently considered to be related to study-product administration
 - Grade 3 clinical AE that is subsequently considered to be related to studyproduct administration with the exception of fever, vomiting, and subjective local and systemic symptoms. For grade 3 infusion-site erythema and/or induration, upon review, the HVTN 143/HPTN 109 PSRT may allow continuation of study-product administration
 - Any grade 3 or 4 lab abnormality confirmed by a repeated value that is subsequently considered to be related to study product;
 - SAE that is subsequently considered to be related to study-product administration

- Clinically significant hypersensitivity or mAb reaction including, but not limited to, type 1 hypersensitivity reaction, urticaria, or serum sickness associated with study-product administration. Consultation with the HVTN 143/HPTN 109 PSRT is required prior to subsequent studyproduct administrations following any hypersensitivity reaction associated with study-product administration
- Investigator determination in consultation with Protocol Team leadership (eg, for repeated nonadherence to study staff instructions)

Participants discontinuing study product for reasons other than HIV acquisition should be counseled on the importance of continuing with the study and strongly encouraged to participate in follow-up visits and protocol-related procedures per the protocol for the remainder of the trial, unless medically contraindicated (see HVTN 143/HPTN 109 SSP).

Participants diagnosed with HIV during the study should be encouraged to participate in follow-up visits as indicated in Section 9.12.

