11.2 Safety reporting

11.2.1 Submission of safety forms to SDMC.

CRS staff must submit all safety forms (eg, solicited AEs, unsolicited AEs, urinalysis, local lab results, and concomitant medications) before the end of the next business day, excluding federal or bank holidays. The forms should not be held in anticipation of additional information at a later date. If additional information is received at a later date, the forms should be updated and resubmitted before the end of the next business day after receiving the new information. For the case of a longer CRS holiday closure, CRS staff must submit the data by the end of the fifth day (local time) after receiving the information, even if this day is a holiday.

For example, if the CRS becomes aware of an AE on Thursday (day 1, the first day), the CRS must submit the data by the end of the next business day, on Friday (day 2). If there is a longer CRS holiday closure, then this AE must be reported no later than the end of day, Monday (day 5). If Monday is a holiday as well, all safety forms still need to be submitted by the end of Monday (day 5).

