• Ab reactions not represented in the DAIDS table to be graded per the "infusion related reaction" row from the Common Terminology Criteria for Adverse Events (CTCAE) from the DHHS (Version 5.0. Published November 27, 2017, available at https://ctep.cancer.gov/protocoldevelopment/electronic_applications/docs/ctca e_v5_quick_reference_5x7.pdf [see also HVTN 143/HPTN 109 SSP]).

All AEs are reported to the SDMC on the appropriate CRF. Clinic staff should evaluate every AE to determine if: (1) the AE meets the requirements for expedited reporting to DAIDS (see Section 11.2.3) and (2) the AE meets the criteria for a safety pause/prompt AE review (see Section 11.5).

Sites are expected to notify HVTN clinical safety staff of any serious safety concern requiring their attention (Table 11-2). Telephone numbers and email addresses are found on the protocol home page on the HVTN Members' site (https://members.hvtn.org/protocols/hvtn143-hptn109). Concerns requiring immediate attention should be communicated by calling the clinical safety phone.

In the case of email notification, clinical safety staff will reply within 1 business day. Serious events that meet pause-rule criteria will be addressed immediately (as outlined in Table 11-2). If email service is not available, the CRS should notify clinical safety staff of the event by telephone, and then submit CRFs.

In addition, CRS investigators are required to submit AE information in accordance with IRB/EC and any applicable RE requirements.

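### Table 11-2 footnote c has no grade limit, so a related, non-serious grade 4 event among 11 of 14 solicited symptoms needs no prompt PSRT review (minor, cheap to fix)

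*Protocol*

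**What the plan says.** **Trial-level trigger (Protocol Section 11.5, Table 11-2).** One row covers related adverse events of grade 4 or 3. The site must email and submit forms immediately, the PSRT is told at once, and it promptly reviews whether to pause. If that review is not finished within 72 hours of notification, not counting weekends and US federal holidays, the trial pauses automatically. Footnote c is attached to the event named in this row: "Does not include subjective solicited AEs (infusion-site pain and/or tenderness, fatigue/malaise, myalgia, arthralgia, chills, headache, nausea [unless IV rehydration required], nonexertional dyspnea, generalized pruritus". Two further symptoms, diaphoresis without explanation and flushing of the face, complete the list. Related serious adverse events have their own rows without the footnote. At grade 4 or 5 they cause an immediate pause.

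**Participant-level stop (Section 7.3.3, under the Part B heading 7.3).** Dosing stops permanently for "Any grade 4 local or systemic solicited or unsolicited AE that is subsequently considered to be related to study-product administration". The separate rule for related grade 3 clinical events applies "with the exception of fever, vomiting, and subjective local and systemic symptoms". For hypersensitivity the section adds: "Consultation with the HVTN 143/HPTN 109 PSRT is required prior to subsequent studyproduct administrations following any hypersensitivity reaction associated with study-product administration".

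**Link between the two.** Section 11.5 says that criteria for an individual's "departure from the schedule of study-product administrations are listed in Section 7.3". It also says that product "administrations may be suspended for safety concerns other than those described in the table, or before pause rules are met" if the PSRT judges that safety may be threatened.

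**Other routes.** Safety forms are due "before the end of the next business day, excluding federal or bank holidays" (Section 11.2.1). Section 11.2.2 expects sites to tell clinical safety staff of serious safety concerns: "Concerns requiring immediate attention should be communicated by calling the clinical safety phone". The PSRT reviews safety reports weekly during the dosing phase (Section 11.6.2).

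**The concern.** Section 7.3.3 separates the two grades: subjective symptoms are excused at grade 3 and not at grade 4. Footnote c does not separate them. A related, non-serious grade 4 nonexertional dyspnea or headache would therefore end that Part B participant's dosing, yet nothing requires prompt notice to the body that decides whether others go on being dosed.

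The setting gives this some weight. Part B opens all five groups at once without enrolment restrictions (Section 11.4.1). Section 4.2.2 states that there are no human PK data for this triple combination, and Section 4.5 says that safety data for VRC01.23LS were still awaited. Several exempt symptoms (chills, flushing, pruritus, shortness of breath) also appear in Section 4.5 among the general risks of monoclonal antibodies. The protocol gives no reason for waiving the trial-level alert at grade 4.

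**Working it through.** The plan has no figure of its own to reproduce here. The check is a count, a side-by-side reading and an order-of-size calculation.

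1. **Count of symptoms.** Section 9.9.1 lists 13 systemic symptoms and 1 local symptom: 13 + 1 = 14. Footnote c names 11, and all 11 are among the 14: 11/14 = 79%. Not exempt are increased temperature, urticaria and nonexertional tachycardia. Nausea is exempt only if IV rehydration is not required, so 10 exemptions are unconditional.

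2. **Scope by grade, for a related, non-serious, listed symptom.**

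| Grade | Section 7.3.3 (one Part B participant) | Table 11-2 with footnote c (trial) |
|---|---|---|
| 3 | Exempt from the stop | Exempt from prompt review |
| 4 | Dosing ends | Exempt from prompt review |

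3. **Can the case arise?** Table 11-2 has one row for related grade 4 serious events and another for related grade 4 events, so the protocol itself provides for grade 4 events that are not serious.

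4. **Does daily monitoring restore the trigger?** Sections 11.1.3 and 11.6.1 direct daily monitoring at events needing expedited reporting and at events that meet the pause or prompt-review criteria. A listed, non-serious grade 4 symptom is neither. The clinical safety specialist and regional medical liaison who do the monitoring are PSRT members (Section 11.1.1), so individual members may see the form early. That does not oblige the PSRT to review it or start the 72-hour clock.

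5. **Timing.** For a non-exempt related grade 4 event, the PSRT is told during working hours or by the next workday morning, and the clock starts. A Friday-morning notification would reach automatic pause on about Wednesday morning, 5 calendar days later. For a listed symptom, full PSRT review is mandated only at the weekly review, up to about 7 days away, with no automatic pause.

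6. **Expected number of events.**
   - Part B: 4 × 8 + 30 = 62 participants; 62 × 2 = 124 infusion visits; 124 × 3 = 372 infusions (three containers per visit, Section 8.4).
   - Whole trial, adding 15 single infusions in Part A: 124 + 15 = 139 visits; 372 + 15 = 387 infusions.
   - Rate from Section 4.4.7.1 (parent antibody VRC01): 1 related grade 4 event in 40,642 infusions.
   - Per infusion: 387 / 40,642 = 0.0095. Per visit: 139 / 40,642 = 0.0034.
   - At an assumed 1 per 100 visits, a figure with no support in the protocol and used only as a high value: 139 × 0.01 = 1.39.

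   The VRC01 rate counts all related grade 4 events and not only listed, non-serious symptoms. It shows the order of size only.

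**The case against.** A reader might infer that Sections 7.3.3 and 11.5 contradict each other. They do not. One governs a single participant's dosing and the other a trial-level alert; Section 11.5 refers the former to Section 7.3, and a site can follow both. Nor were the lists written to match. Section 7.3.3 exempts fever and vomiting at grade 3 and footnote c exempts neither, so there the trial-level rule is the stricter one. Section 7.3.3 also stops individuals for reasons outside Table 11-2, such as HIV acquisition. That a participant's dosing has stopped therefore does not by itself show that the trial should be alerted.

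A reader might also infer that such an event would go unseen for a week. That is too strong. PSRT members do the daily monitoring, forms arrive by the next business day, and sites are expected to report serious concerns. A self-reported reaction above mild is generally seen by a clinician within 48 hours unless it is improving or resolved (Section 9.9), and hypersensitivity needs PSRT consultation before that participant is dosed again. Infusion reactions with these same symptoms were recorded as unsolicited events in the earlier trial described in Section 4.4.5; recorded that way, they fall outside footnote c.

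Finally, many grade 4 events may be serious and so pause the trial anyway. The protocol does not reproduce the grade 4 definitions for these symptoms, so the share that would be non-serious cannot be established from it.

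All of this stands and keeps the point minor. What remains is that none of these routes requires prompt PSRT review of the event or starts the automatic-pause clock. PSRT discretion helps only once the PSRT knows.

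**Conclusion.** The reading of the text is firm: footnote c covers grade 4, and Section 7.3.3 confines its exemption for subjective symptoms to grade 3. This is a minor, inexpensive safety improvement and not an error or a contradiction.

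The gap is narrow. It needs an event that is related, grade 4, non-serious, recorded as solicited and on the list of 11. The effect on dosing that makes it notable arises only in Part B, because Part A gives one dose; there, Section 11.4.1 sends any related event of grade 3 or higher to the Safety Monitoring Board before Part B opens. The expected number of events is about 0.003 to 0.01 over the trial, assuming that the VRC01 rate carries over to these products. That assumption is untested for this combination.

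**What to change.** In Table 11-2, begin footnote c with *Does not include grade 3 subjective solicited AEs*, and leave the list and the nausea/IV-rehydration qualifier as they are. Symptoms exempt from prompt review would fall from 11 of 14 to 0 of 14 at grade 4 and stay at 11 of 14 at grade 3. The Safety Monitoring Board review in Section 11.4.1 needs no change.

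The cost is two added words and at most an occasional extra PSRT notification and review: about 0.003 to 0.01 expected over the trial, or about 1.4 at the assumed 1 per 100 visits. No new data collection is needed.

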11.6 Review of cumulative safety data

Routine safety review occurs at the start of enrollment and then throughout the study.

Reviews proceed from a standardized set of protocol-specific safety data reports. These reports are produced by the SDMC and include queries to the CRSs. Events are tracked by internal reports until resolution.

11.6.1 Daily review

Daily safety reviews are routinely conducted by HVTN Core for events requiring expedited reporting to DAIDS, and events that meet safety pause criteria or prompt HVTN 143/HPTN 109 PSRT AE review criteria.

11.6.2 Weekly review

During the study-product administration phase of the trial, the HVTN 143/HPTN 109 PSRT reviews clinical safety reports on a weekly basis and conducts calls to review the data, as appropriate. Following the visit 8 weeks post–final study-product administration, less frequent reporting and safety reviews may be conducted at the discretion of the HVTN 143/HPTN 109 PSRT. HVTN LOC reviews reports of clinical and laboratory AEs. Events identified during the review that are considered questionable, inconsistent, or unexplained are referred to the CRS CC for verification.

11.7 Study termination

NIAID reserves the right to terminate or curtail a clinical study for any reason, including but not limited to the following (reference: https://grants.nih.gov/grants/guide/rfa-files/RFA-AI-12-012.html):

- Risk to participant safety
- The scientific question is no longer relevant or the objectives will not be met (ie, slow accrual)
- Failure to comply with GCP, all applicable regulations, or terms and conditions of award
- Occurrence of unforeseen drug safety issues or data from preclinical studies indicate a presence of unanticipated toxicity

- Risks that cannot be adequately quantified
- Ethical concerns raised by the local community or local medical care/healthcare authorities
- Failure to remedy deficiencies identified through site monitoring
- Substandard data
- Reaching a major study endpoint substantially before schedule with persuasive statistical significance.

This study may also be terminated early by the determination of the HVTN 143/HPTN 109 PSRT, a pertinent national regulatory authority, NIH, the Office for Human Research Protections (OHRP), or study-product developer(s). In addition, the conduct of this study at an individual CRS may be terminated by the determination of the IRB/EC and any applicable RE.

12 Protocol conduct

This protocol and all actions and activities connected with it will be conducted in compliance with the principles of GCP (ICH E6[R2]), and according to DAIDS, HVTN, and HPTN policies and procedures as specified in the network-specific MOP, DAIDS Clinical Research Policies, and Standard Procedures Documents, including procedures for the following:

- Protocol registration, activation, and implementation;
- Informed consent, screening, and enrollment;
- Study-participant reimbursement;
- Clinical and safety assessments;
- Safety monitoring and reporting;
- Data collection, documentation, transfer, and storage;
- Participant confidentiality;
- Study follow-up and close-out;
- Quality control;
- Protocol monitoring (on-site or remote) and compliance;
- Advocacy and assistance to participants regarding negative social impacts associated with the trial;
- Risk-reduction counseling;
- Specimen collection, processing, and analysis;
- Exploratory and ancillary studies and substudies, and
- Destruction of specimens.

DAIDS, HVTN, and HPTN policies and procedures are available for review by any IRB/EC/RE upon request.

Any policies or procedures that vary from DAIDS, HVTN, or HPTN standards or require additional instructions (eg, instructions for randomization specific to this study) will be described in the HVTN 143/HPTN 109 SSP.

